#### 19 Data ownership, use of results and publication policy

All data generated in this study will centralised and belong to CNM. A final copy of the database containing all the data will be held at CNM. The database can be shared with the other collaborators, as mutually agreed basis. Sharing the data with other parties is subject to the approval of the principal investigator.

Any data published in the peer-reviewed medical literature will protect the identity of the subjects. This trial will be registered in a web based protocol registration scheme. The results from all study sites will be published in a peer-reviewed journal. All those who have made a substantial contribution will be co-authors on publications. All the research findings will be disseminated to policy makers for an informed decision on drug policy for the treatment of malaria and other researchers.

#### 20 Budget

Human resources	
	WHO (US\$)
• professional scientific staff (4 persons)	
Director: $500$ \$ x $10$ month = $5000$	5,000
PI: $900$ \$ x $10$ months = $8000$	9,000
Co-PI: $500$ \$ x $10$ months = $5000$	5,000
Epidemiologist: $300$ \$ x $10$ months = $3000$	3,000
technical staff (10 persons)	
CNM Medical Doctors (2 persons): $600\$ \times 2 \times 8$ months = $9600$	9,600
$CNM\ Lab\ tech\ (2): 600\$ $x\ 2\ x\ 8\ months = 9600$	9,600
• local support (6 persons)	
MD/MA (2 persons): $450$ \$ x 2 x 8 months = $6400$	6,400
Lab tech (2 persons): $300$ \$ x 2 x 8 months = $4800$	4,800
Nurse (2 persons): $300 \times 2 \times 8 \text{ months} = 4800$	4,800
Sub-total	57,200
Field-based transportation	
• Motor rental for following up the patients (2 motors)	3,200
Motors: $200\$ x 2 x 8 months = 3200$	
Sub-total	3,200
Equipment and supplies	
• equipment	
Hematocrit centrifuge	
Stethoscopes & blood pressure	

 
Hematocrit apparatus
 
	
o Glucose apparatus	1,800
o Scales	
o Battery	
o Lamps	
• Supplies	1,680
• Supplies  • Reagent	1,000
Methanol	

Urine test

	
Medicine (antipyretic, analgesic,	
diazepam, others)	
o Slide boxes	
Researcher Kits	
Silues     Parenteral Fluid	
	2 900
operational costs (space rental, communication)     Sub-total	3,800 7,280
	7, 280
Contingency fees for clinical trials	l

o ethical review	450
o registration	
o liability insurance	
Sub-total Sub-total	450
Patient costs (145 P. falciparum cases)	
Work loss: $145 \times 3\% \times 9$ times = $3262.5$	3,263
Food cost: $145 \times 3\$ \times 3 = 1087.5$	1,088
Travel Cost enrolled patients: $145$ \$ x $10$ \$ x $7$ times = $8700$	8,700
Referral fee: $145$ \$ x $15 = 2175$	2,175
Hospital fee: 145 x 10\$ = 1450	1,450
Fee for non-enrolled patients: $40 \times 10.12\$ = 405$	450
Patient costs for recurrent infection	
- Assumption: 10 patients will experience treatment failure: treated with $A+M$ & follow up until 42 days: 10 patients x 129 $\$$ = 1290 $\$$	1,290
Sub-total	18,370
Technical assistance	
(training, document translation, support to research institutions, capacity building)	
o Training	1,000

 
Translation (protocol, forms and etc.)
 
	800
Sub-total	1,800
Supervision	,
PI/CNM Director,Co-PIs, field monitoring officer	
4 resource persons $x 20$ \$ $x 5 days x 15 times = 5600$	5,600
One driver: $20\$ x 5$ days $x 15$ times = $1600$	1,600
Fuel: 157.14\$ x 14 times = 2200	2,200
Sub-total	9,400
	7,400
Quality assurance system	2.000
(data validation, slides cross-check): 250\$ x 8 months = 2000	2,000
Sub-total	2,000
Data management	
(data entry, data analysis, report writing): 300\$ x 8 months = 2400	2,400
Sub-total	2,400
Laboratory support	
(genotyping)	
Liver function tests (145 patients): $145 \times 45.52$ \$ = $6600$	6,600
Sample shipment from Battambang & Pursat to IPC	800
Sub-total	7,400
Result dissemination	

 
Publication in Peer review journal
 
	
Miscellaneous	500
Sub-total	500
Grand Total	110,000

# **Study sites**

[figure not shown]

Figure 1: Sentinel sites

# APPENDIX 1: ADVERSE EVENT OF SPECIAL INTEREST: DRUGS AND THE LIVER

#### **Checklist for Serious Liver Reactions:**

- stop study drug. Stop herbal remedies and concomitant medications if they are not medically necessary.
- urgently collect urine, blood, or relevant biological fluids for PK (within 24 hours of last dose, or 3 half-lives, whichever is longer), diagnostic tests
- additional history and review of medical records
- discuss details with the patients, in particular any concomitant meds, OTC meds, herbal remedies, prior exposure, previous episodes etc
- documentation of laboratory values, ECG tracings, pathology reports, PK etc
- ensure appropriate medical attention, including move to hospital Emergency Department or ICU, specialist consultation, etc
- arrange appropriate follow up for investigations
- Safety Review Team to review aggregate data from available sources for underlying trends
- Contact safety department or other internal and external experts for advice

Documentation needed in the event of a clinically significant elevation in one or more liver function tests

• Liver function test results that are codified as adverse events, and/or elevations that occur rapidly or exceed multiples of the upper limit of normal, merit further inquiry on the part of the investigator. The laboratory tests that are relevant in this regard include ALT (SGPT), AST (SGOT), GGT, and alkaline phosphatase (ALP). Examples of elevations that may require more intensive inquiry on the part of the investigator include an ALT or AST value that exceeds 5.0 times the upper limit of normal or an ALT or AST value that exceeds 3.0 times the upper limit of normal and a total bilirubin value that exceeds 2 times the upper limit of normal (Hy's law). With massive hepatic injury, the ability of the liver to excrete conjugated (or direct) bilirubin diminishes. Therefore, the presence of ALT >3xULN and concomitant bilirubin >2xULN (>35% direct), in the absence of elevated alkaline phosphatase or biliary injury, suggests significant liver injury, mandating the need for immediate drug cessation and specialist/hepatologist consultation, and follow up of liver chemistries and prothrombin time twice weekly until values normalize or substantively improve.

The laboratory will have standing orders to analyze the value of ALP isoenzymes in situations where ALP values exceed twice the upper limit of normal. Similarly, the central laboratory will have standing orders to fractionate total bilirubin into its direct and indirect components in situations where the total bilirubin value exceeds 2 times the upper limit of normal.

• The investigator should obtain a hepatitis panel (Anti-HAV IgM, Anti-HBc IgM, HBsAg, and hepatitis C RNA), hepatitis E IgM antibody (if subject outside N. America, or has travelled outside N. America in prior 3 months); cytomegalovirus (CMV) testing polymerase chain reaction (PCR) testing, pp65 antigen, or IgM antibody; Epstein Barr virus (EBV) viral capsid antigen IgM antibody; serum

- creatinine phosphokinase (CPK) and lactate dehydrogenase (LDH). If bilirubin >2 x ULN, bilirubin should be fractionated to obtain % direct bilirubin.
- When ALT >3xULN and bilirubin >2xULN (>35% direct bilirubin on fractionation), obtain: antinuclear antibody, anti-smooth muscle antibody, Type 1 anti-liver kidney microsomal antibodies.

If laboratory values are returned that meet the above described criteria, and if there is a possibility of past or recent exposure to infectious hepatitis, and/or a history of high-risk behaviours that would place the subject at risk for infectious hepatitis.

If laboratory values are returned that meet the above-described criteria, the investigator should attempt to document the following in the investigator comment log of the CRF prior to contacting the sponsor:

- The subject's age, gender and weight.
- The date (and visit number) on which the blood sample was obtained.
- The Randomization date as well as the dose level that the subject is currently taking, and the duration of exposure to that dose level. The exact date on which the subject took the last dose of the study medication and an objective assessment should be obtained of the subject's compliance with the study medication.
- The specific abnormal laboratory values, as well as those of each of the other LFTs noted above (regardless of value) and, when relevant, results of isoenzyme or fractionation analyses. The investigator should also document the corresponding laboratory values at screening/baseline.
- Other notable abnormalities in laboratory values (*e.g.*, complete blood count, eosinophilia, or electrolyte abnormalities, if present).
- The dates and nature of any relevant adverse events (e.g., jaundice) that occurred since Randomization, with particular attention to hypotension, fever, rash, hepatitis symptoms (e.g. appearance or worsening of fatigue, nausea, anorexia, nausea, emesis, abdominal pain), or other adverse events that might have occurred in close proximity to the elevation in the laboratory value(s) of interest.
- Any associated physical findings (including results of any exams or evaluations, including heart rate, blood pressure, temperature, and abdominal exam).
- The use of concomitant medications (*e.g.*, acetaminophen, herbal products) since Randomization, as well as the dates of exposure to the concomitant medication(s). Please include any nutritional supplements, vitamins and/or herbal preparations that the subject might have taken during this time frame.
- A statement concerning whether the subject has consumed alcohol since the time of Randomization, with a description of frequency and intensity, if relevant. A blood alcohol level should be obtained if the subject's history and/or clinical presentation suggest proximal use or intoxication with alcohol.
- Any history on the subject's part of prior elevations in any of the relevant laboratory values. Provide actual dates and laboratory values.
- Any history on the subject's part of a past or recent history of exposure to known factors that can cause, or are associated with, elevations in liver function tests. Examples of these factors include alcohol abuse and/or dependence, hepatitis (infectious or chemical), infectious mononucleosis, gallbladder disease, liver disease of any kind, jaundice, myocardial infarction, heart failure and/or episodes of hypotension.
- Any family history of hepatitis (from any cause) or hepatotoxicity from medications.

Please contact the medical monitor if you have questions about the most appropriate course of action, and/or if you have questions as to whether the subject should be referred to a specialist for further evaluation.

It is anticipated that the investigator will follow any subject with clinically significant elevations of one or more liver function tests until there is clear evidence that the value(s) have stabilized and/or normalized. In addition, an explanation should be provided for any subjects that are lost to follow up.

Possible Hy's Law case following the FDA Guidance on Drug Induced Liver Injury: Premarketing Clinical Evaluation dated July 2009 A possible Hy's law case is defined as a subject with any value of ALT or AST above 3xULN together with an increase in bilirubin to a value higher than 2xULN and NOT associated to an ALP value higher than 2xULNA decision on medical and scientific grounds is required to assess whether an immediate notification of an event is warranted in other situations, such as medically important events which are not life-threatening, fatal or cause hospitalization, but could endanger the patient or could rendered necessary an intervention to prevent one of the above conditions to develop.

Remark: Examples of such events are intensive care in the emergency room or at home to treat a bronchospasm; a haematological dyscrasia; convulsions or an asymptomatic increase ALT ( $\geq 10 \text{ x ULN}$ ) not causing hospitalisation, or the development of drug addiction or abuse

TABLE 1: STUDY SCHEDULE

	D0	D1	D2	D3	D4	D7	D14	D21	D28	D35	D42	REPf		olumes
Screening													(ml) per time	
Written informed consent	X												adult	Child
Assign participant ID	X												≥16 yrs	<16yrs
Participant's history	X													
Symptoms checklist	X	X	X	X	X	X	X	X	X	X	X	X		
Vital signs	X	X	X	X	X	X	X	X	X	X	X	X		
Temperature	X	X	X	X	X	X	X	X	X	X	X	X		
General Examination	X	X	X	X	X	X	X	X	X	X	X	X		
Study Drug administration														
PYR-Artesunate	X	X	X											
Laboratory Procedures														
#Malaria blood film	X	X	X	X	X	X	X	X	X	X	X	X	0.5	0.5
HCT or Hb	X	X	X	X	X	X	X	X	X	X	X	X	0.03	0.03
Filter paper blots	X											X	0.3	0.3
FBC	X			X		X	X		X		X	X	1	1
Biochemistry	X			X	_	X	X		X		X	X	1	1
	X					X						X	0.5	0.5

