# 9. Follow up (see table 1 in appendix)

- All patients will have a blood smear examined daily during the first week by microscopy until parasite clearance (2 consecutive negative slides on two consecutive days; both asexual and sexual stages). A negative blood slide will be defined as parasite count negative per 1000 WBC in two consecutive days. The sample on day 3 will be taken as close as possible to 72h after the initial blood smear.
- Blood biochemistry and basic haematology on D0, D3, D7 D14, D28 and D42. Tests for: AST/ALT, total bilirubin and alkaline phosphatase. If values increase, a confirmation test will be done within 48 hours where practical and clinically indicated. Regarding liver function tests (LFT), any elevation of ALTx3ULN on day 3 not having returned to baseline by day 7 will be followed up and repeated on day 28 and 42. A specific monitoring of LFT will be performed for any patient in which ALT values are greater than 3xULN combined with a bilirubin greater than 2xULN (Hy's law), or if ALT has risen to above x5ULN, irrespective of other accompanying abnormalities (cf Appendix 2 on "Adverse Event of Special Interest: drugs and the liver"). In such cases, LFT will need to be repeated twice a week until values return to baseline. Hy's law cases will need to be reported as a SAE (See Section 14.2). Total blood volume per time point for biochemistry and haematological assessments will be 2 mL.

*Time windows for follow-up visits:* 

The time-window for the visit on Day 7 is + 1 days, for the visits on Days 14 - 35 is -1 to +1 days and for D42 is -1 to +1 days. If patients do not attend for follow-up a home-visitor from the study team will try to locate the patient and bring them to the clinic.

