# 12.3 Adverse Events of Special Interest:

An adverse event of special interest (AESI) is an adverse event for which on-going monitoring is appropriate within the context of the study. These events necessitate complementary examinations in order to characterize and understand them.

AESIs in this study can be related to:

- Hepatotoxicity
- Neurotoxicity/seizures
- Cutaneous reactions/photo toxicity

The study team, as well as the relevant referral facilities, should be trained to take particular notice of symptoms/signs suggestive of the AESIs in this study:

- 1) clinical and biological signs of possible hepatotoxicity such as:
- fatigue, nausea, abdominal pain, dark urine, putty or mastic coloured stools, jaundice (vellowing of the whites of the eyes or skin) and itching
- ALT value >5xULN or ALT value >3xULN AND total bilirubin value >2xULN
- 2) clinical signs of possible cardio-toxicity
- Palpitations
- Seizures
- Pounding/pain in the chest area
- Fainting/Syncope.
- 3) clinical signs of possible neurotoxicity/seizures such as:
- Seizures
- Dizziness
- Pins and needles sensations
- Visions disturbance
- Difficulties coordination
- Tinnitus
- 4) clinical signs of possible cutaneous reactions/photo toxicity such as:
- Urticaria
- angioedema
- · Skin lesions
- · Itching pruritus
- Discoloration
- Dermatitis

In all the cases of hepatotoxicity, confirmed by the PI / investigators, the sponsor. Notification will occur through the use of an ad hoc AESI form.

The patients with the following elevations may require more intensive inquiry on the part of the investigator: ALT value that exceeds 5.0 times the upper limit of normal or ALT value

that exceeds 3.0 times the upper limit of normal AND a total bilirubin value that exceeds 2 times the upper limit of normal (Hy's law).

The investigator should then consult the treating Cambodian physician to obtain an hepatitis panel (Anti-HAV IgM, Anti-HBc IgM, HBsAg, and hepatitis C RNA), hepatitis E IgM antibody, cytomegalovirus (CMV) testing polymerase chain reaction (PCR) testing, pp65 antigen, or IgM antibody; Epstein Barr virus (EBV) viral capsid antigen IgM antibody; In addition, serum creatinine phosphokinase (CPK) and lactate dehydrogenase (LDH) would need to be measured. The treating Cambodian physician will ensure proper referral in case a diagnosis of non-malaria or study drug related pathology.

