## **APPENDIX 4. SERIOUS ADVERSE EVENT REPORT FORM**

Serious adverse event report form			
Health centre name:	Study number:		
Locality:	Patient identity number:		
District:	Date of visit (dd-mmm-yyyy):		
Province:	Follow-up day:		
Demographic dat	a		
Date of birth (dd-mmm-yyyy): or estimate years	ed age: in: months or		
Height (cm): Weight (kg):			
Sex: Male Female			
If female, is the patient pregnant?   Yes   No   No	t sure		
If pregnant, provide the date of the last menstrual period	d (dd-mmm-yyyy):		
Serious adverse ev	ent		
Type of event:			
☐ Death			
Life-threatening			
☐ Hospitalization or prolongation of hospitaliz	ation		
Permanent disability			
Congenital anomaly or birth defect			
Date of occurrence (dd-mmm-yyyy):			
Describe the serious adverse event (include all relevant	laboratory results):		
Describe how the reaction was treated:			

	Serious	adverse ev	ent report for	rm (page 2)	
Comments (e.g. relevions) other laboratory data, reappeared after reinting	whether rea				
		O	Outcome		
Recovered	completely				
☐ Not yet reco	overed				
Recovered y  If patient recovered, p	_	erm consequ		vv).	
1		suspected o	of causing the	serious adverse	event as well as all
concomitant medicines)					
Brand name, batch number, manufacturer name (list suspected medicine first)	Daily dose	Route	Start date	End date	Indications for use

Reporting officer		
Name:		
Qualification:		
Address:		
Phone:		
Fax:		
Email:		
Signature:	Date:	

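### The protocol gives conflicting definitions of Hy's law (on AST and on ALP), so it does not settle which liver cases must be reported as SAEs

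*Protocol*

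**What the plan says.** **Section 9 (Follow up).** Closer liver monitoring starts when "ALT values are greater than 3xULN combined with a bilirubin greater than 2xULN (Hy's law), or if ALT has risen to above x5ULN". AST and ALP play no part. The same paragraph adds "Hy's law cases will need to be reported as a SAE (See Section 14.2", and sends the reader to an appendix titled "Adverse Event of Special Interest: drugs and the liver", which it numbers 2.

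**Section 12.3 (Adverse Events of Special Interest).** The laboratory sign of hepatotoxicity is "ALT value >5xULN or ALT value >3xULN AND total bilirubin value >2xULN". The section later repeats the ALT-only combination and labels it Hy's law.

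**Appendix 1 (drugs and the liver).** Three formulations appear:

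- The examples that may call for closer enquiry are an "ALT or AST value that exceeds 5.0 times the upper limit of normal", or ALT or AST above 3xULN with total bilirubin above 2xULN. The second is labelled Hy's law and carries no ALP condition.
- Shortly after, significant liver injury is described by ALT only above 3xULN, with bilirubin above 2xULN (more than 35% direct) and ALP not elevated.
- The closing definition of a possible Hy's law case takes "any value of ALT or AST above 3xULN" with bilirubin above 2xULN, provided ALP is not above 2xULN.

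**The concern.** Hepatotoxicity is the first-listed event of special interest, and liver enzyme elevation is the drug risk that the ethics section describes. Hy's law is the one liver category to which the protocol attaches an SAE duty. If its definition changes from page to page, two sites can see the same laboratory result and one reports an SAE while the other does not. The conflict runs in both directions. The AST wording in Appendix 1 adds cases compared with section 9, and the ALP condition removes some. The section 9 rule is therefore not just a short form of the appendix.

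**Working it through.** There is no stated figure to reproduce. The check is to write each definition as a rule and see where the rules part.

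**Inputs.** The thresholds listed above from sections 9 and 12.3 and Appendix 1. Divide ALT into three bands (up to 3, 3 to 5, above 5 xULN), AST likewise, bilirubin into two (up to 2, above 2 xULN) and ALP into two (up to 2, above 2 xULN). That gives 3 x 3 x 2 x 2 = 36 patterns. These are kinds of patient, not frequencies.

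**Hy's law.**

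| Source | Rule | Patterns that qualify |
|---|---|---|
| Sections 9 and 12.3 | ALT >3x and bilirubin >2x | 2 x 3 x 1 x 2 = 12 |
| Appendix 1, closer-enquiry sentence | ALT or AST >3x, and bilirubin >2x | (9 - 1) x 1 x 2 = 16 |
| Appendix 1, possible Hy's law case | ALT or AST >3x, bilirubin >2x, ALP not >2x | (9 - 1) x 1 x 1 = 8 |

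The ALT-only liver-injury sentence is left out of the count. It gives no multiple for elevated ALP, adds a direct-bilirubin fraction, and does not itself use the Hy's law label.

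**Where sections 9 and 12.3 and the closing definition disagree.**

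- Case under sections 9 and 12.3 only: ALT >3x, bilirubin >2x, ALP >2x, any AST. 2 x 3 = 6 patterns.
- Case under the closing definition only: ALT up to 3x, AST >3x, bilirubin >2x, ALP up to 2x. 1 x 2 = 2 patterns.
- Total in dispute: 6 + 2 = 8. Both rules accept 12 - 6 = 6 patterns.

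Appendix 1 also disagrees with itself. Its closer-enquiry sentence calls the high-ALP patterns Hy's law and its closing definition does not: 16 - 8 = 8 patterns.

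**AESI or enquiry trigger (5x arm, or 3x with bilirubin).**

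- Section 12.3, ALT only: ALT >5x gives 3 x 2 x 2 = 12 patterns. ALT 3 to 5x with bilirubin >2x gives 3 x 2 = 6. Total 18.
- Appendix 1, ALT or AST: either enzyme >5x gives 5 x 2 x 2 = 20 patterns. The higher enzyme at 3 to 5x with bilirubin >2x gives 3 x 2 = 6. Total 26.
- The 26 - 18 = 8 extra patterns all come from AST. ALP plays no part in this trigger in either place.

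**Does any other text settle it?**

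- Section 14 covers slide quality control and has no 14.2.
- Appendix 2 is the case screening form. The liver text is Appendix 1.
- The SAE criteria in section 12.2 do not name Hy's law.
- Nothing states which definition governs reporting.

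**Can the ALP condition be checked from the forms?** ALP is scheduled in section 9. The liver tables in the case report forms for days 0, 3, 7 and 28, however, list only total bilirubin, albumin, ALT and AST.

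**The case against.** The strongest reply is that the SAE duty is stated only in section 9, in the same paragraph as an ALT-only criterion, and that Appendix 1 never calls a Hy's law case an SAE. On that reading section 9 governs and there is no conflict between two SAE rules. The factual part stands: a reader might infer two competing SAE rules, and the protocol contains only one. But section 9 also points to the liver appendix, which holds the only passage set out as a formal case definition, and that passage gives a different set of patients. The reader is not told which to use.

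Other stronger readings are also not supported:

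- **Twice-weekly testing on AST.** Appendix 1's own twice-weekly sentence is ALT-only, so on AST it agrees with section 9.
- **Damage to the main secondary endpoint.** That endpoint is absolute values and change from baseline of the liver tests. It uses no Hy's law threshold.
- **An ALP condition on the AESI trigger.** There is none. For that trigger the conflict is AST alone, and Appendix 1 words its version as examples that may need enquiry.
- **The SAE form.** It has no box for a Hy's law case without hospital admission, but that would be so under any definition. It is a separate, minor matter.

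There are partial safeguards. All adverse events are recorded whatever their seriousness, and Appendix 1 expects significant elevations to be followed until they stabilise or normalise. These protect the record and the follow-up. They do not settle whether the event is sent as an SAE.

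**Conclusion.** The inconsistency is real and should be corrected. Two kinds of patient are affected on Hy's law: those with AST but not ALT above 3xULN and raised bilirubin, and those with ALT above 3xULN, raised bilirubin and ALP above 2xULN. Sections 9 and 12.3 differ from the closing definition of Appendix 1 on 8 of 36 patterns. The AESI trigger differs on a further comparison of 8 patterns, all through AST.

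The documents do not say how often such patterns occur among the planned 145 patients, so the number of misreported cases cannot be estimated. Confidence bounds for a rare event in 145 patients would not measure it either. The efficacy analysis is unaffected. The conclusion assumes only that the appendix is meant to inform section 9, as the section's own cross-reference indicates.

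**What to change.** 1. Reconcile section 9, section 12.3 and the three formulations in Appendix 1 into one case definition that states whether AST and ALP enter. The choice of clinical rule belongs to the sponsor and its safety advisers.
2. Use that definition for SAE and AESI reporting and for any tabulation of Hy's law cases. State in the same way whether AST enters the AESI trigger.
3. Correct the two cross-references in section 9: the appendix number, and the Section 14.2 that does not exist.
4. If ALP enters the definition, add ALP to the liver tables of the case report forms.

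The cost is a wording amendment and possibly one row in each liver table. ALT, AST, total bilirubin and ALP are already scheduled, so no extra test is needed for these criteria.
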